an unstructured covariance matrix to take into account the within-patient correlation between repeated measures over time. The predictors in the model will include a dummy coded time effect and an indicator variable for Tele-Self CBT interacting with the time effect. The mean structure of the model will have the form: $Y = \beta_0 + \beta_1 * 6\text{wk} + \beta_2 * (\text{month6}) + \beta_3 * (\text{Tele-Self CBT1} * 6\text{wk}) + \beta_4 * (\text{Tele-Self CBT1} * \text{month6}) + \beta_5 * (\text{age}) + \beta_6 * (\text{baseline ISI})$, and model parameters will be estimated using the SAS procedure MIXED (Cary, NC). Note that this model is a constrained intercept model, which assumes a common baseline mean¹⁰⁹. We will formally evaluate the intervention effect by testing that β_3 differs from zero and report the mean difference and corresponding 95% confidence interval. A mean difference significantly less than zero provides evidence that Tele-Self CBT patients have greater improvements in ISI at 8 weeks. The model will also include centered, stratification variables of age ($\leq 50/ > 50$ years), baseline ISI ($\leq 20/ > 20$), *mental health disorder status (presence/absence)*, *psychotropic medication (use/non-use)* and *sleep medication (use/non-use)* as recommended in the CPMP guidelines¹⁰⁸.

Hypothesis 2: Relative to Health Education, participants randomized to receive Tele-Self CBT1 will have greater improvements in subjective sleep (per diary SOL, WASO, and SE), objective sleep (per actigraphy WASO, TST, and SE), fatigue, depression symptoms, and QOL at 8 weeks. As described above, sleep parameters (both diary and actigraphy) are recorded daily during each of the three 2-week assessment periods. Daily values will be averaged across each 2-week period, resulting in three repeated continuous outcomes for each of the sleep parameters, including baseline, 8 weeks, and 6 months. Treatment group differences at 8 weeks and 6 months for these subjective and objective sleep measures will be tested via the same general linear model as specified above for the primary hypothesis. Similarly, the fatigue, depression symptoms and QOL outcomes will also be analyzed with a general linear model as specified above for the primary hypothesis. Again, PROC MIXED will be used to estimate and test the appropriate model parameters, and the mean difference and corresponding 95% confidence intervals will be reported.

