E.3 Sample Size Considerations (Aims 1 & 2): Our sample size estimates are based on the Hypothesis 1 primary outcome – Insomnia Severity Index. Because this is a longitudinal study with repeated measurements on each subject, mean change is estimated with increased precision. In sample size calculations, the increase in precision can take into account the correlation between repeated measures. With Tele-Self CBT1, we anticipate seeing smaller effects than might be seen with in-person CBT1. Additionally, our comparison group receives more than usual care, again leading to smaller effects. In a recent meta-analysis, the effect of CBT1 on ISI yielded large Hedge's g effect sizes of 0.98. Conservatively, we then base our sample size estimates on an effect size of 0.5; this translates into a relative mean improvement on the ISI of at least 2.8. Assuming a baseline SD of 5.8, a repeated-measures correlation of 0.6 (both quantities estimated from previous studies^[37,52,54,114]), and a type-I error of 5%, we will need to have 73 patients in each arm to detect a relative mean improvement of 3 on the ISI with 90% power. To account for dropout and possible deviations from our assumptions, we plan to enroll and randomize 100 patients in each arm (total sample size n=200). With this sample size, we will also have adequate power to examine our secondary outcomes. For example, previous studies of SE show a baseline SD of 12.5 and repeated-measures correlation of 0.7. With our projected sample size, we will have 90% power to detect a relative improvement in SE of at least 6.2. The repeated-measures design option in PASS¹¹⁵ was used for all calculations.

E.4 Data Analysis (Aim 3)

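### E.3 attaches 73 per arm at 90% power to an ISI difference of 3, but the figure matches the 2.8 given just before it; the n behind the sleep-efficiency figure should also be stated (minor)

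*Combined protocol and SAP*

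**What the plan says.** Section E.3 (Sample Size Considerations) bases the trial size on the primary outcome, the ISI. It takes "an effect size of 0.5; this translates into a relative mean improvement on the ISI of at least 2.8". The next sentence gives the inputs, "Assuming a baseline SD of 5.8, a repeated-measures correlation of 0.6" with a 5% type I error, and concludes "we will need to have 73 patients in each arm to detect a relative mean improvement of 3 on the ISI with 90% power". Section E.1 makes tests two-sided, and section C.5 sets 1:1 allocation.

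The number is then raised: "To account for dropout and possible deviations from our assumptions, we plan to enroll and randomize 100 patients in each arm". No dropout rate is given; 73 of 100 corresponds to a 27% loss.

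For secondary outcomes E.3 says "With this sample size, we will also have adequate power to examine our secondary outcomes". Its example is sleep efficiency (SE): "previous studies of SE show a baseline SD of 12.5 and repeated-measures correlation of 0.7", followed by "With our projected sample size, we will have 90% power to detect a relative improvement in SE of at least 6.2". All calculations are credited to the repeated-measures option in PASS. The contrast, the number of measurements and the variance formula are not given.

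**The concern.** Two adjacent sentences give different ISI targets, and the required n depends on the square of the target. Moving from 2.8 to 3 changes n by a factor of (2.8/3)² = 0.871, a reduction of about 13%. One n at one power cannot belong to both. The SE sentence has a related difficulty. It comes straight after the plan for 100 per arm, so a reader will take 6.2 as the difference detectable with 200 participants.

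E.3 is the only justification given for randomising 200 people. As written, a reader cannot reproduce it, and a final report could repeat a target difference that does not match its sample size.

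**Working it through.** **Inputs.** ISI: SD 5.8, correlation ρ = 0.6, power 90%, 73 per arm (E.3). Two-sided α = 0.05 (E.1). SE: SD 12.5, ρ = 0.7, difference 6.2 (E.3).

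**Formula.** n per arm = 2 f [(1.960 + 1.282) × SD / δ]², where f is the variance factor that carries the repeated-measures correlation. The unrounded sum of the two normal quantiles is 3.2415. Results were also checked with the noncentral t distribution (df = 2n − 2).

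**Reproducing the 73.** At ρ = 0.6 a change score, 2(1 − ρ), and an average of two measurements, (1 + ρ)/2, both give f = 0.80.

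- δ = 2.8: 2 × 0.80 × (3.2415 × 5.8 / 2.8)² = 72.1, so 73 per arm (74 by t). Power at 73 is 90.3% (90.0% by t).
- δ = 3: 2 × 0.80 × (3.2415 × 5.8 / 3)² = 62.8, so 63 per arm (64 by t). Power at 73 is 93.7% (93.5% by t).

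**Other standard factors at ρ = 0.6, n per arm for 90% power (normal / t):**

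| Factor | f | δ = 2.8 | δ = 3 | Power at 73 for δ = 3 (normal) |
|---|---|---|---|---|
| Change score or two-measure average | 0.80 | 73 / 74 | 63 / 64 | 93.7% |
| Correlation unused | 1 | 91 / 92 | 79 / 80 | 87.8% |
| Three-measure average, (1 + 2ρ)/3 | 0.733 | 67 / 68 | 58 / 59 | 95.4% |
| Baseline-adjusted, 1 − ρ² | 0.64 | 58 / 59 | 51 / 52 | 97.4% |

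Only f = 0.80 with δ = 2.8 returns 73. For 73 per arm to fit δ = 3, f would have to be about 0.92 to 0.93, which none of these formulas gives at ρ = 0.6. A one-sided test or 80% power does not rescue it: for δ = 3 the largest n under these factors is then 65 or 59.

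**Effect-size scaling.** 0.5 × 5.8 = 2.9, which at f = 0.80 needs 68 per arm (69 by t). So 73 fits neither 2.9 nor 3. E.3 does not say that 5.8 is the SD used to scale the 0.5, so this is a matter for clarification only.

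**SE figure.** The difference detectable at 90% power is 3.2415 × 12.5 × √f × √(2/n). At ρ = 0.7 the two formulas that coincided for the ISI separate.

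- Two-measure average, f = 0.85: 6.18 at 73 per arm; 5.28 at 100 per arm.
- Change score, f = 0.60: 5.19 at 73 per arm; 4.44 at 100 per arm.

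So 6.2 reproduces at 73 per arm with the two-measure average, the same rule that gives 73 for an ISI difference of 2.8. At 100 per arm the listed factors, evaluated at ρ = 0.7, give 4.1 to 5.7. Reaching 6.2 there would need f = 1.17, more variance than a single unadjusted comparison. Power for 6.2 at 100 per arm is 96.7% at f = 0.85 and 93.9% at f = 1.

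**The case against.** The best defence is rounding. Against an SD of 5.8, 2.8 is 0.48 SD and 3 is 0.52 SD, and both round to 0.5. The 3 may simply be 2.8 to the nearest whole ISI point, with 73 correct for the intended target. That is probably what happened, and it determines the repair: the difference should be corrected, not the n. The inconsistency still stands, because the printed n and power do not belong to the printed difference.

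The factor of 0.80 is also inferred. This stands, and the correction should follow the PASS output. It also limits any statement about direction: if the correlation were ignored, 73 per arm would give 87.8% power for 3. That reading is unlikely, since E.3 says the correlation was used.

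On SE, the projected sample size can fairly mean those left after dropout, and power for 6.2 exceeds 90% at 100 per arm on every factor tried. The sentence is therefore unclear about n but not shown to be wrong.

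A reader might go further and infer that the 90% is not the power of the primary 8-week test. E.3 does not identify its contrast, and the analysis in E.2 is described differently: "Note that this model is a constrained intercept model, which assumes a common baseline mean". But silence about the contrast does not establish a mismatch. Nor can a reliable power for that test be computed from the documents, because E.3 gives only a baseline SD. If the follow-up SD were 10% or 20% larger (assumed values, ρ still 0.6), a change-score comparison at 73 per arm would have 86.7% or 82.6% power for 2.8 by the t calculation. No figure for that test is proposed here.

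**Conclusion.** The 73-per-arm sentence is wrong as written: on the stated inputs and f = 0.80 it matches a difference of 2.8 and not 3. The discrepancy is 9 to 10 patients per arm, or about 93.5% power against the stated 90%. The inferred factor is supported by the fact that one rule reproduces both the 73 and the 6.2. On that factor the error is conservative.

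It does not follow that the trial is too small or too large. With complete data, 100 per arm gives 96.8% power for 2.8 at f = 0.80 and 92.7% even with the correlation unused, so no shortfall is shown. Nor do the documents suggest that 63 or 64 per arm was ever the intended calculation. Severity is minor. Confidence is high for the mismatch between 2.8 and 3, and lower for the n behind the SE figure, which is a request for clarification.

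**What to change.** Keep 200 participants. After checking the PASS output, change 3 to 2.8 in the 73-per-arm sentence so that E.3 uses one ISI target throughout, and state the SD that scales the 0.5. If the output shows a different target or variance formula, restate the sentence from the output.

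Name the n behind the SE figure, for example: *with 73 evaluable per arm, 90% power to detect 6.2*. If 100 per arm was meant, the value on the same two-measure rule is about 5.3.

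The cost is a check of existing output and edits to two or three sentences. Enrolment, the primary test and trial conduct do not change.

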The target population for this trial is treatment-seeking Veterans with Insomnia from the Durham Veteran's Affairs Healthcare System. Because few VA PCPs routinely document insomnia in the medical record⁷⁹, identifying patients with insomnia in the EHR is challenging. Prescribed sleep medications are the most common PCP response to an insomnia complaint, although some patients are referred for CBTI. Consistent with the larger literature, we found no difference between Veterans prescribed sleep medications and those who were not prescribed sleep medications in terms of improvements in insomnia severity ($f=.15$, $p=.70$) following participation in group based CBTI at the Durham VAMC⁸⁰. Thus, we have defined treatment-seeking Veterans with Insomnia as those who are: a) prescribed sleep medications; b) diagnosed with insomnia; or c) referred for clinic-based CBTI (but not yet treated).

Table 1. Eligibility Criteria Assessment: Methods and Measures

Eligibility Criteria	Assessment Method
Level 1 (L1)-Data Pull and Chart Review	
Inclusion	
≥ 18 years of age	EHR data pull
Insomnia Diagnosis OR prescribed sleep medications OR referred for CBTI	EHR data pull & record review
Exclusion	
Psychotic DO; Bipolar DO; Substance Use; Alcohol Abuse	EHR data pull
Dementia; Cognitive Impairment; Epilepsy; Seizure DO	EHR data pull
Severe OSA with treatment non-adherence	EHR record review
Unstable housing and/or no/unreliable telephone	EHR record review
Unstable Co-morbid Sleep DO; and current or prior participation in CBTI	EHR record review
No current/prior CBTI participation	EHR record review
Nursing Home Residence	EHR record review
Level 2 (L2)-Phone Screening, Consent & Enrollment	
Inclusion	
Insomnia Disorder diagnostic criteria are met per ICSD-3	DSISD Insomnia DO Module ⁶
Insomnia Severity Index score of ≥ 10	ISI ⁷
Exclusion	
Severe OSA with treatment non-adherence (when unclear from EHR review)	Phone Screening
Unstable housing and/or no/unreliable telephone (when unclear from EHR review)	Phone Screening
Excessive daytime sleepiness	Epworth Sleepiness >15
Nighttime or Rotating Shift Work w/in the last year	Phone Screening
Confirm no current/prior CBTI participation	Phone Screening
Severe Depression and Suicidality	PHQ-8 >19 and/or SI
Current Recreational Drug Use	Drug Use Screener endorsed
Nursing Home Residence (to complement information from EHR chart review)	Phone Screening

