her clinical work in the Behavioral Sleep Medicine (BSM) clinic; specifically, those who have been referred to the BSM Clinic and/or patients awaiting the availability of a provider to begin treatment. This will be accomplished by reviewing the chart of patients who have been referred to the BSM clinic with an insomnia complaint, and reviewing the BSM Clinic electronic waiting list/s. [name] will record in an excel file located here

(R:\Insomnia_Self_CBTI_Trial_IRB_2147\Data\Databases\Tracking Database\Physician Referrals) the name of patients meeting initial eligibility criteria (i.e., diagnosed with insomnia, prescribed sleep medications, and/or referred to the BSM clinic for insomnia treatment).

Research staff will then follow the recruitment procedures described in Approach 1 above, beginning with chart review.

Approach 3-Flyer Posting and Brochure Placement

Approach 3 involves placement of recruitment flyers in the VA approved research recruitment bulletin boards located throughout the hospital and CBOC clinics. We have also created a brochure about the study that may be distributed in clinics.

Exclusion criteria: 1) Severe Obstructive Sleep Apnea with treatment non-adherence; 2) unstable co-morbid sleep disorder determined via chart review (e.g., rule out for Narcolepsy, rule out for Shift Work Disorder); 3) current or prior participation in CBTI; 4) excessive daytime sleepiness; 5) nighttime or rotating shift work within the last year; 6) psychotic disorder diagnosis; 7) bipolar disorder diagnosis; 8) recreational substance use/abuse; 9) current alcohol abuse; 10) severe depression or suicidality; 11) dementia diagnosis; 12) cognitive impairment; 13) epilepsy or seizure disorder 14) lack of proficiency in the English language; 15) hearing impairment that impedes telehealth intervention; or lack of stable housing and/or no access to a telephone.

Rationale for Inclusion/Exclusion Criteria:

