Insomnia Diagnosis: The Duke Structured Interview for Sleep Disorders (DSISD)⁸¹ is a structured clinical interview for screening and diagnosing sleep disorders and is being revised to concord with newer diagnostic nosologies (DSM-V)¹⁴ and the ICSD-3⁸². The DSISD Insomnia Disorder module will be administered to ensure that Insomnia Disorder diagnostic criteria are met. **Insomnia Severity Index (ISI)**⁹⁷: The ISI is recommended as the standard for self-reported insomnia symptoms, with a score of 10 or more to indicate active insomnia symptoms⁹⁶.

Contraindicated Hypersomnia Disorders: The Epworth Sleepiness Scale (ESS)⁸⁴ will be used to exclude those with occult obstructive sleep apnea (OSA) and those for whom sleep restriction therapy would be contraindicated due to either untreated sleep apnea or hypersomnia in the absence of apnea. The ESS is an 8-item measure assessing one's self-rated typical sleep propensity in daily life and is sensitive for daytime sleepiness across a range of settings and research paradigms⁸⁶. An ESS score of >15 indicates the possibility of undiagnosed or untreated sleep apnea or narcolepsy and will be used to exclude potential study participants⁸⁴.

Severe Depression: We will use the Patient Health Questionnaire-8⁸⁷ to screen Veterans for severe depression. The validity of the PHQ-8 was established using data from the 2006 Behavioral Risk Factor Surveillance Survey⁸⁷. Veterans scoring in the severe depression range (>19) will be ineligible for the study but may become eligible at a later date if symptoms decline. [name] will ensure that medical providers of Veterans scoring in the severe depression range are aware of their mental health status. Veterans endorsing suicidality will be managed in accordance with the Suicide Safety Plan

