Substance Use/Abuse: We will define alcohol abuse as documentation in the medical record of current alcohol abuse. Those with the two most recent AUDIT-C administrations documented in the medical record and scored as negative will be eligible for the study. The AUDIT-C⁸⁸, a well-validated 3-item screener for alcohol abuse used in VA⁸⁹ and primary care settings⁹⁰, to screen out those who are actively abusing alcohol. We will use the clinical scoring criteria for men and women respectively. We will use a single item to screen out those engaged in recreational drug use⁹¹. This item was found to be highly sensitive (100%) and moderately specific (73.5%) for detecting those with a drug use disorder and had good sensitivity (81.8%) and specificity (72.5%) for laboratory-based evaluation of drug use⁹¹.

Table 3. Assessment Measures

	Items	Timing		
		BL	8 weeks	6 months
Background-EHR Data				
VA Sleep & Psychotropic Medications	n/a	•		
Medical Conditions	n/a	•		
Mental Health Conditions	n/a	•		
Background-Self Report				
Demographic Characteristics	18	•		
Medical Conditions	up to 16	•		
Primary Outcome				
Insomnia Symptom Severity: ISI	7	•	•	•
Secondary Outcomes				
Actigraphy (WASO, TST and SE)	n/a	•	•	•
Sleep Diary (SOL, WASO and SE)	8	•	•	•
Fatigue: Multidimensional Fatigue Inventory	20	•	•	•
Depression: PHQ-8	8	•	•	•
Chronotype: MEQ	19	•	•	•
Trauma-related Sleep Disturbances (PSQI Addendum)	10	•	•	•
International Physical Activity Questionnaire	11	•	•	•

Glasgow Sleep Impact Index	7	•	•	•
Insomnia Treatment Knowledge Questionnaire	10	•	•	•
Ask if participant has accessed CBTI Coach and/or Path to Better Sleep	2		•	•

Outcome Measures

Outcome measures will be collected by phone by the project's research assistant (RA) at baseline, 8 weeks, and 6 months. Copies of self-report outcome measures are listed below.

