
F. Handling of Unexpected and Adverse Events

F.1 Risk/Benefit Assessment

This study involves a low risk cognitive-behavioral intervention. There are no investigational drugs or devices being tested in this study. The risks of this intervention are no greater than those incurred during a standard clinical intervention for insomnia. The main risk of study participation is the possibility of becoming upset when answering personally probing questions on the study questionnaires, or during engagement in the intervention. Participants will have the option of refusing to answer distressing questions or withdrawing from the study at any time without adversely affecting their ongoing care. Hence, the risks of such discomfort are mitigated by the options offered to participants. The PI will report any serious, unexpected, and study-related adverse event or unanticipated problem to the patient's provider and local IRB according to the institution's requirements (5 business days). The IRB will review all adverse events during continuing review, which will likely occur annually. All adverse events will be reported in the annual report to the VAMC IRB.

The Qualitative study involves interviews that will be approximately 20-30 minutes or

focus groups will be approximately 1 hour. Risks of discomfort is assessed to be low. Participants are informed they can refuse to answer questions or drop out at any point of participation.

F.2 Adverse Events

While we do not anticipate adverse events related to study activities, all adverse events that do occur will be reported per Durham VAMC requirements. All Serious, Unanticipated and Related adverse events will be reported to IRB within 5 business days of hearing of the event. All other adverse events will be reported at continuing review.

F.3 Safety Plan for Suicidal Ideation

During study screening and each assessment period, a Research Assistant (RA) will administer the Patient Health Questionnaire (PHQ-8) to assess depression. If patients endorse suicidal ideation or express clinical warning signs of elevated risk of self-harm (e.g., severe depression), study staff will gather more information from the participant, including information about suicidal plan, means, intent, and history of suicidal behavior, by administering a structured screener, the P4 Screener, to assess the potential for suicide risk.

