Coded data with direct identifiers removed (i.e., name, address, telephone numbers, SSN, DOB) will be placed at VINCI. We will be using REDCap a VA Intranet Web application

approved by VA and run by VA VIReC. The REDCap software is web-based but participants will be interviewed over the phone and data will be entered by study staff behind the VA's firewall. The data are housed on a VA Informatics & Computing Infrastructure (VINCI) Server. Data from the Actigraph device will be downloaded to our local server behind the VA firewall at `\v06.med.va.gov\HSDR\Insomnia_Self_CBTI_Trial_IRB_2147`. HSR&D servers are located in a secured area at [name]. All VA research personnel who have access to VHA records are instructed, in accordance with VA policy, on the requirements of Federal privacy and information laws and regulations, VA regulations and policies, and VHA policy. All study personnel who are VA employees working within the VA system have fulfilled all required HIPAA and other VA security and privacy policy training requirements and have agreed to follow guidelines pertaining to the protection of patient data. All research staff sign VA Rules of Behavior, and all study staff are up to date with VHA Privacy Policy Training and the VA Office of Cyber and Information Security Awareness Training Course. The data security and privacy procedures summarized in that course include logging off or locking the computer when walking away from it; no sharing of access codes, verify codes or passwords; not allowing anyone else to use the computer under one's password; and disposing of sensitive information using VA-approved methods (e.g., shredder bins). Access to study data will be removed for all study personnel when they are no longer part of the research team.

This is a minimal risk intervention for insomnia and we do not anticipate any safety issues related to the intervention. Patient activity will be monitored for Serious adverse events during the intervention period by intervention nurses.

Screening, baseline, and outcomes data will be collected via telephone at baseline, after the intervention (week 6) and at the 6-month follow-up. Suicidality will be assessed across the same timepoints, as part of the PHQ-8. The Suicide Safety plan will be implemented for patients endorsing suicidality during completion of the PHQ-8 at any point in study conduct, as discussed above.

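### F.5 relies on the PHQ-8 to detect suicidality, but the standard eight-item form has no self-harm item and no measure listed for baseline or follow-up elicits ideation

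*Combined protocol and SAP*

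**What the plan says.** F.5 (Data and Safety Monitoring) gives the data-collection points as baseline, after the intervention and 6 months, and then says: "Suicidality will be assessed across the same timepoints, as part of the PHQ-8". The trigger for action follows: "The Suicide Safety plan will be implemented for patients endorsing suicidality during completion of the PHQ-8 at any point in study conduct".

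F.3 (Safety Plan for Suicidal Ideation) covers screening and each assessment period: "a Research Assistant (RA) will administer the Patient Health Questionnaire (PHQ-8) to assess depression. If patients endorse suicidal ideation", or show warning signs, of which severe depression is the example given, staff administer the P4 Screener.

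At entry, Table 1 gives the assessment method for the severe depression and suicidality exclusion as "PHQ-8 >19 and/or SI". The exclusion list in C.3 has the matching entry, "10) severe depression or suicidality". C.8 sets the score rule: "Veterans scoring in the severe depression range (>19) will be ineligible for the study".

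Table 3 lists "Depression: PHQ-8" with 8 items, at baseline, 8 weeks and 6 months. It has no row for suicidality.

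**The concern.** The eight-item form of the Patient Health Questionnaire is the one that leaves out the self-harm item. If so, F.5 assigns the detection of ideation to a scale that cannot register it, and makes the Safety Plan wait for an answer to a question that is not on the form. Staff who follow F.5 to the letter would complete the PHQ-8 and consider suicidality assessed.

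What is at stake is participant safety. Section B says insomnia plays a causal role in suicidality and presents the study as responsive to a suicide-prevention priority. Ideation is therefore foreseeable in this population.

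**Working it through.** No power, alpha or effect-size figure is involved. The check is to ask, for each contact, what in the plan would elicit ideation from every participant.

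**1. Does the PHQ-8 elicit it?** The item wording is not in the documents, so the answer rests on an assumption: the trial uses the standard form, which has no self-harm item. The text is consistent with this. Table 3 counts 8 items. C.8 and F.3 describe the scale only as a depression measure. The nine-item form is not mentioned anywhere. Table 1 and exclusion 10 set ideation beside the depression criterion, not inside it.

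**2. Does any other listed measure elicit it?** Counting the entries in the Measures column of Table 4:

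| Contact | Entries | Name an ideation question | PHQ-8 listed |
|---|---|---|---|
| Screening | 7 | 0 | yes |
| Baseline | 12 | 0 | no |
| 8 weeks | 12 (one for the intervention arm only) | 0 | yes |
| 6 months | 11 | 0 | yes |

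Table 3 adds none. Table 4's baseline list omits the PHQ-8, although Table 3 and F.3 both require it then. Table 4 is therefore not a full record, and these counts show what the plan names, not what staff ask.

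**3. Does the P4 elicit it?** Only at a second stage. Under F.3 it follows endorsed ideation or a warning sign.

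**4. Do the other contacts elicit it?** The nurses who make the six weekly calls are trained to respond to ideation that comes up during a call. F.4 deals with Veterans who report it themselves. Both act on disclosure, and neither specifies a question.

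**5. Who is missed on a literal reading?** All four of these must hold: ideation is present, the PHQ-8 is 19 or below, there is no other warning sign, and the Veteran does not volunteer it. A score above 19 is in the severe range by C.8's definition and so reaches the P4 through F.3's severe-depression example. However, C.8 makes scores above 19 ineligible at screening, so everyone enrolled entered at 19 or below. At follow-up the score-based route opens only for those who have worsened past that cut-off.

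**The case against.** The strongest reply is that the plan clearly intends ideation to be asked about. Table 1 lists it as a screening criterion apart from the score, exclusion 10 repeats it, and F.5 commits to assessing it throughout. An ideation question may simply be asked in the same block as the PHQ-8, with F.5 worded loosely. Appendices 2a-2f, cited in C.3 for Level 2 screening, and the copies of outcome measures mentioned in C.8 are not in the file, and either could contain it. This stands. A reader might infer that nobody in the trial is ever asked about ideation, or that the suicidality exclusion goes unassessed. The documents do not support that: material missing from the file is not missing from the plan, and Table 1 implies that the question is put at phone screening.

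A reader might also extend the charge to C.8, whose PHQ-8 paragraph ends "Veterans endorsing suicidality will be managed in accordance with the Suicide Safety Plan". That sentence names no instrument for suicidality and does not say it is endorsed on the PHQ-8. The wrong-instrument point belongs to F.5 alone.

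A further reply is that the form's content is not printed. That is so, and it is why the content is stated as an assumption. It concerns what a named, standard instrument contains, not the result of an outside study, and the text agrees with it. If the trial's version does carry a self-harm item, the remedy shrinks to saying so.

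The safeguards are also real: the screening exclusion, the P4 for warning signs, trained nurses, the crisis-line hand-off and clinician follow-up. They narrow the gap. They do not replace a question, because after screening each depends on disclosure or on visible signs.

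**Conclusion.** The point holds against F.5 as written. Its assessment and trigger rule names a scale that, in its standard form, has no item on which suicidality could be endorsed. No measure listed for baseline, 8 weeks or 6 months fills the gap. The gap is clearest at those three assessments. At screening the plan has the criterion but does not name the question.

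The conclusion rests on two assumptions: that the standard eight-item form is used, and that staff follow F.5 and the tables literally. If an unseen script already asks about ideation at every assessment, no safety gap remains and only F.5 and the tables need correcting. If the question is in the screening scripts alone, the gap at the later assessments remains. With no ideation prevalence in the documents, no count of affected Veterans can be given.

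This should be fixed on patient-safety grounds. The existing safeguards and the unseen scripts keep it from being more serious than that. The ISI analysis, the sample size and the depression outcome are unaffected.

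**What to change.** - At screening and at each assessment, ask one named stand-alone ideation question. Alternatively, give the nine-item form and score items 1-8 as the PHQ-8, so that the depression outcome and the >19 cut-off do not change.
- List that question in Tables 1, 3 and 4, and add the missing PHQ-8 to Table 4's baseline list.
- Amend F.3 and F.5 so that endorsing the named question triggers the P4, and remove from F.5 the statement that the PHQ-8 assesses suicidality. C.8 needs only a cross-reference.
- If an existing script already asks about ideation, name that question in F.5 and the tables, and confirm that it is asked at baseline, 8 weeks and 6 months.

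The cost is one extra question per screening or assessment call, a short script and protocol amendment, and somewhat more P4 follow-ups through the existing pathway. No new staff are needed.
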